9.0 Procedures Involved

University at Buffalo Institutional Review Board (UBIRB)

Office of Research Compliance | Clinical and Translational Research Center Room 5018
[name]
UB Federalwide Assurance ID#: FWA00008824

PROTOCOL TITLE: Effects of adrenocorticotropic hormone (Acthar gel®) on recovery from cognitive relapses in MS.

9.1 Describe and explain the study design.

9.2 Provide a description of all research procedures being performed and when they are performed, including procedures being performed to monitor subjects for safety or minimize risks.

Initial referral will be initiated by treating physicians. Following confirmation of the subject's relapse status and/or the presence of new supratentorial GAD enhancing lesions, patients deemed eligible for Acthar treatment will be screened for symptoms of infection and evaluated by their treating physician. If the patient agrees, the clinician will contact the research coordinator with the referral.

At this time, all participants will undergo study eligibility screening and consent by a Clinical Research Project Coordinator. The project coordinator or a designated member of the research team will meet, in person, with the participant to discuss the study objectives and procedures, so that he/she can make an informed decision regarding voluntary study participation. Participants will have an opportunity to ask questions regarding the study, procedures, etc. At this time, the study coordinator will administer the SDMT to the relapsing patient. The study coordinator will give this score to another study personnel. At this time the other

University at Buffalo Institutional Review Board (UBIRB)

Office of Research Compliance | Clinical and Translational Research Center Room 5018
[name]
UB Federalwide Assurance ID#: FWA00008824

PROTOCOL TITLE: Effects of adrenocorticotrophic hormone (Acthar gel®) on recovery from cognitive relapses in MS.

study personnel will check the patient's baseline SDMT score. If this score is less than or equal to a 3 point decline, the patient will be deemed eligible for the study. Participants who choose to enroll in the study will then be asked to sign and date a consent form in front of the Study Coordinator.

As described above, enrolled subjects will complete the full cognitive baseline assessment [CVLT2 Learning → BVMTR Learning → SDMT → PASAT → DKEFS Sorting → CVLT2 Delayed Recall → BVMTR Delayed Recall → NAART]. Here the SDMT will be administered a second time to complete the run in for the information processing speed [IPS] composite. Participants will then be guided to complete other patient report questionnaires [BDIFS, FSS MSIS, MSNQ]. Finally, measures of motor function and clinical status will be assessed (EDSS and MSFC).

Acthar Gel will then be administered by a research coordinator to the relapsing patient in accordance with the recommendations set forth in the package insert. The dosage may be individualized according to the medical condition of each patient. Frequency and dose of the drug may be determined by considering the severity of the disease and the initial response of the patient. Acthar will be provided through the study.

As cognitive relapses are typically milder (compared to physically focused relapses) subjects will be initially dosed for 5 days and pending clinical response or adverse events treatment may be continued for the full 2 weeks in the opinion of the investigator. At study enrollment participants will be instructed on self-administration procedure and supplied with a 5-day course of Acthar® Gel (5ml/80 IU). Medication will be administered through either subcutaneous or intramuscular self-injection (selected by the patient). Patients will be instructed by trained clinical staff on self-administration and will self-administer the first injection under observation in the clinic.

The neuropsychological evaluation takes approximately 45 minutes to complete. The neurological exam takes about 15 minutes. Training and administration of the drug takes about 15 minutes. The neuropsychological assessment will be repeated at 90 days. All participants will be given \$200 at the completion of the study. At the time of consenting, each participant will complete a W-9 form. Checks will be mailed from our billing department directly to the participant's address of choice.

The treating neurologist will be responsible for identifying patients agreeing to treatment with the study drug and for insuring that the EDSS is

University at Buffalo Institutional Review Board (UBIRB)

Office of Research Compliance | Clinical and Translational Research Center Room 5018
[name]
UB Federalwide Assurance ID#: FWA00008824

PROTOCOL TITLE: Effects of adrenocorticotropic hormone (Acthar gel®) on recovery from cognitive relapses in MS.

conducted in a valid manner. Examining technicians will be responsible for administering the neuropsychological testing battery. The Research Coordinator will be responsible for consenting patients, and contacting them on day 7 and day 30 to evaluate for concomitant medications and adverse events. The PI will be responsible for consenting patients, coordinating the database, conducting statistical analysis, coordinating recruitment efforts, and presenting the data.

A detailed clinical assessment will precede enrollment and only patients who agree to be treated with Acthar will be approached for participation. For patients that qualify, Acthar will be provided through the study.

All medications prescribed for patients will be monitored as per PI recommendations. Patients will be evaluated and monitored and all SAEs will be reported to the local IRB within required timelines.

9.3 Describe procedures performed to lessen the probability or magnitude of risks.

A detailed clinical assessment will precede enrollment and only patients who agree to be treated with Acthar will be considered for participation. All serious adverse events will be reported to Mallinckrodt (formerly Questcor) and local IRB within required timelines. The study protocol will be approved by the local Health Sciences Institutional Review Board at the University at Buffalo.

The Research Coordinator will be responsible for consenting patients, and contacting them on day 7 and day 30 to evaluate for concomitant medications and adverse events. Subjects will also be given the telephone contact information for study staff in case of any late-emerging side effects. Any adverse events will be reported to the PI, the patient's treating neurologist, and the Health Sciences Institutional Review Board at the University at Buffalo Immediately.

Prior to any testing under this protocol, including screening tests and evaluations, all subjects will sign an informed consent form that complies with the requirements of both 21 CFR Part 50 and HIPAA before entering the study. Or, a consent form that complies with the requirements of 21 CFR Part 50 and a separate HIPAA compliant authorization form for the use of and disclosure of the subject's protected health information (PHI) will be obtained from the subject in accordance with local practice and regulations.

University at Buffalo Institutional Review Board (UBIRB)

Office of Research Compliance | Clinical and Translational Research Center Room 5018
[name]
UB Federalwide Assurance ID#: FWA00008824

PROTOCOL TITLE: Effects of adrenocorticotrophic hormone (Acthar gel®) on recovery from cognitive relapses in MS.

The background of the proposed study and the benefits and risks of the procedures and study will be explained to the subject. A copy of the informed consent document signed and dated by the subject will be given to the subject. Confirmation of a subject's informed consent will also be documented in the subject's medical records prior to any testing under this protocol, including screening tests and evaluations.

The subject will not be identified by name in any study reports, and these reports will be used for research purposes only. Every effort will be made to keep the subject's personal medical data confidential.

All medications prescribed for patients will be monitored as per PI recommendations. Patients will be evaluated and monitored and all SAEs will be reported to the local IRB within required timelines.

SAEs and unexpected AEs will be collected by the investigator. An SAE is defined as an adverse event that meets any of the following criteria: results in death, is life-threatening, requires hospitalization or prolongation of existing hospitalization, results in disability/incapacity, is a congenital anomaly/birth defect, or is an important medical event. An unexpected adverse event is an AE either not previously reported or for which the nature, seriousness, severity, or outcome is not consistent with the current Investigator's Brochure. Additionally, the site should report if a patient becomes pregnant during the study and track until an outcome is known. AEs will be documented, evaluated and treated by the investigators according to standard of care (decisions regarding treatment will be made by Investigator [name]). All SAEs will be reported to the Institutional Review Board (IRB), as well as RTI-HS (on behalf of Mallinckrodt, formerly Questcor), within 5 business days (unless a different notification schedule is required by the IRB). In the event of a patient death, initial notice will be provided to the IRB and RTI-HS within 24 hours and full details regarding the case will be provided within 5-calendar days. Safety reporting guidelines and relevant forms are supplied in Appendix 1.

9.4 Describe all drugs and devices used in the research and the purpose of their use, and their regulatory approval status.

Acthar Gel will be administered in accordance with the recommendations set forth in the package insert. The dosage may be individualized according to the medical condition of each patient. Frequency and dose of the drug may be determined by considering the severity of the disease and

University at Buffalo Institutional Review Board (UBIRB)

Office of Research Compliance | Clinical and Translational Research Center Room 5018
[name]
UB Federalwide Assurance ID#: FWA00008824

PROTOCOL TITLE: Effects of adrenocorticotropic hormone (Acthar gel®) on recovery from cognitive relapses in MS.

the initial response of the patient. Acthar Gel will be provided to the patient through the study.

As cognitive relapses are typically milder (compared to physically focused relapses) subjects will be initially dosed for 5 days and pending clinical response or adverse events treatment may be continued for the full 2 weeks in the opinion of the investigator. At study enrollment participants will be instructed on self-administration procedure and supplied with a 5-day course of Acthar® Gel (5ml/80 IU). Medication will be administered through either subcutaneous or intramuscular self-injection (selected by the patient). Patients will be instructed by trained clinical staff on self-administration and will self-administer the first injection under observation in the clinic.

9.5 Describe the source records that will be used to collect data about subjects. (Attach all surveys, scripts, and data collection forms.)

Source records include:

- Expanded Disability Status Scale (EDSS)
- Symbol Digit Modalities Test (SDMT)
- Paced Auditory Serial Addition Test (PASAT)
- California Verbal Learning Test Second Edition (CVLT2)
- Brief Visuospatial Memory Test- Revised (BVMT-R)
- MS Functional Composite (MSFC)
- Beck Depression Inventory Fast Screen (BDIFS)
- Fatigue Severity Scale (FSS)
- Multiple Sclerosis Impact Scale (MSIS)
- MS Neuropsychological Screening Questionnaire (MSNQ)
- North American Adult Reading Test (NAART)

9.6 What data will be collected including long-term follow-up.

The above-mentioned data will be collected at months 0 and 3.

9.7 For HUD uses provide a description of the device, a summary of how you propose to use the device, including a description of any screening procedures, the HUD procedure, and any patient follow-up visits, tests or procedures.

University at Buffalo Institutional Review Board (UBIRB)

Office of Research Compliance | Clinical and Translational Research Center Room 5018
[name]
UB Federalwide Assurance ID#: FWA00008824

PROTOCOL TITLE: Effects of adrenocorticotropic hormone (Acthar gel®) on recovery from cognitive relapses in MS.

N/A

10.0 Data and Specimen Banking

10.1 If data or specimens will be banked for future use, describe where the data/specimens will be stored, how long they will be stored, how the data/specimens will be accessed, and who will have access to the data/specimens.

Neuropsychological testing data and clinical outcome measures will be maintained in de-identified participant charts. These charts will be stored in a locked cabinet and entered into a password-protected database. Appropriate legal guidelines regarding retention of records will be followed. Identifiable data will be destroyed at the earliest possible point. The subject will not be identified by name in any study reports, and these reports will be used for research purposes only. Every effort will be made to keep the subject's personal medical data confidential. Stored data will be accessed only by the PI and/or designated research staff. The use of stored, de-identified data is undetermined at this time.

10.2 List the data to be stored or associated with each specimen.

Neuropsychological testing data and clinical outcome measures will be stored for each participant.

10.3 Describe the procedures to release data or specimens, including: the process to request a release, approvals required for release, who can obtain data or specimens, and the data to be provided with specimens.

Identifiable data will not be released to any outside sources. Investigator will refer to the Clinical Trial Agreement for details regarding the disclosure of study results.

11.0 Data Management

11.1 Describe the data analysis plan, including any statistical procedures.

Data will be processed by trained research assistants blind to study hypotheses. Analysis will be conducted using SPSS 22.0. Analysis strategy will be repeated measures analysis of variance where baseline, day 0 and day 90 scores are compared. Analysis of variance will be used

University at Buffalo Institutional Review Board (UBIRB)

Office of Research Compliance | Clinical and Translational Research Center Room 5018
[name]
UB Federalwide Assurance ID#: FWA00008824

PROTOCOL TITLE: Effects of adrenocorticotropic hormone (Acthar gel®) on recovery from cognitive relapses in MS.

to compare the magnitude of change between day 0 and 90 between the MS patients treated with Acthar and the previously collected controls. Analysis of variance will also be used to compare the magnitude of cognitive recovery after corticosteroid treatment to that after Acthar treatment.

The difference between the means at Day 0 and Day 90 will be used to calculate Cohen's d for each group. To facilitate analysis, all data will be normalized using a large previously published control sample.¹³ All tests will be performed based on an alpha of 0.05. Net effect sizes removing estimated practice effects will be calculated using Cohen's d.

11.2 Provide a power analysis.

The selection of 30 as the target enrollment is based on the previously completed study of 25 relapsing and 25 stable MS patients. Five additional patients are planned in order to increase the power of subsequent analyses. A power analysis based on the observed effect of corticosteroids in the relapsing group of $d = .56$ with 30 participants will be powered $>85\%$ to detect effects of a moderate magnitude from Acthar.

11.3 Describe the steps that will be taken to secure the data (e.g., training, authorization of access, password protection, encryption, physical controls, certificates of confidentiality, and separation of identifiers and data) during storage, use, and transmission.

All clinical and neurometric assessments will be conducted under the supervision of the PI. All members of research team will complete relevant training programs and courses, including but not limited to: HIPAA, CITI and GRP.

NP testing data will be maintained in locked filing cabinets within a locked room (4085) within UBMD Neurology at the Conventus Center, [name]. Participants will be assigned study identification numbers at enrollment. The NP testing database will be kept without identifying information on an encrypted computer and matched to online survey information using the assigned code number.

The subject will not be identified by name in any study reports, and these reports will be used for research purposes only. Every effort will be made to keep the subject's personal medical data confidential.

11.4 Describe any procedures that will be used for quality control of collected data.

University at Buffalo Institutional Review Board (UBIRB)

Office of Research Compliance | Clinical and Translational Research Center Room 5018
[name]
UB Federalwide Assurance ID#: FWA00008824

PROTOCOL TITLE: Effects of adrenocorticotrophic hormone (Acthar gel®) on recovery from cognitive relapses in MS.

A Data and Safety Monitor (DSM), comprised of an independent member of the MS-care community without a conflict of interest with the study, will be selected for this study. It will be comprised of a medical professional who is not involved with the conduct of the trial. The DSM will be responsible for evaluating scientific issues related to the study. The DSM will meet with the investigators upon the enrollment of every 10 participants and/or in the event that any adverse, serious or non-serious event occurs, and/or every 6 months or more frequently if deemed necessary. The DSM will be given a detailed progress report before the scheduled meeting. This report will contain safety data summaries: recruitment, visit schedules, missed visits, patient compliance, demographics, outcomes, and adverse events. In addition, copies of all Adverse Events will be included in the report. Also, the DSM will be able to request specific information and analyses to be used for monitoring purposes at any time during the study.

The roles and responsibilities of the DSM will include the following:

- Review protocol, informed consent documents, plans for data safety and monitoring;
- Evaluate study progress, including periodic assessments of data quality and other factors that may affect study outcome;
- Consider external factors such as scientific or therapeutic developments that may impact the safety of the participants or the ethics of the trial;
- Protect the safety and scientific progress of the trial;
- Make recommendations to the Investigators regarding continuation, termination, or other modifications to the study based on observed beneficial or adverse events of the treatment under study.

11.5 Describe how data and specimens will be handled study-wide:

Neuropsychological testing data will be kept in a locked room and in a locked cabinet. After data scoring and entry, neuropsychological testing files will be de-identified by blacking out identification information. Databases will be password protected.

11.6 What information will be included in that data or associated with the specimens?

University at Buffalo Institutional Review Board (UBIRB)

Office of Research Compliance | Clinical and Translational Research Center Room 5018
[name]
UB Federalwide Assurance ID#: FWA00008824

PROTOCOL TITLE: Effects of adrenocorticotrophic hormone (Acthar gel®) on recovery from cognitive relapses in MS.

Each participant will be assigned a study identification number. Data points related to information processing speed, memory, executive functioning, depression, fatigue, and disability will be collected.

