7.0 Study Timelines

7.1 *Describe the duration of an individual subject's participation in the study.*

This is a prospective, open-label study of Acthar administered as treatment for an acute cognitive relapse. Primary and secondary endpoints will be collected prior to Acthar administration and at 3-month follow-up. Comparison will be made to a stable MS control group.

7.2 *Describe the duration anticipated to enroll all study subjects.*

Enrollment of all study participants is expected to take 4 years (48 months).

7.3 *Describe the estimated date for the investigators to complete this study (complete primary analyses)*

Completion of this study, including primary analysis, is expected within 5 years.

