8.0 Study Endpoints

8.1 *Describe the primary and secondary study endpoints.*

Primary measures will include: Symbol Digit Modalities Test,¹⁴ Brief Visualspatial Memory Test- Revised,¹⁵ Paced Auditory Serial Addition Test,¹⁶ and the Multiple Sclerosis Functional Composite (MSFC).²³ These tests are some of the strongest indicators of clinically relevant cognitive change available in MS.

The Symbol Digit Modalities Test (SDMT) will be used to measure visual processing speed. This test presents a stimulus key of numbers paired with abstract symbols at the top of a page. Participants scan the page below the key which has rows of symbols without the paired numbers. The task is to generate the associated numbers orally as fast as possible. We will employ the Rao oral adaptation²⁴ of the SDMT as the oral presentation has been deemed most appropriate for use with a potentially motor impaired population.¹²

University at Buffalo Institutional Review Board (UBIRB)

Office of Research Compliance | Clinical and Translational Research Center Room 5018
[name]
UB Federalwide Assurance ID#: FWA00008824

PROTOCOL TITLE: Effects of adrenocorticotropic hormone (Acthar gel®) on recovery from cognitive relapses in MS.

The Paced Auditory Serial Addition Test (PASAT)²⁵ 3 sec interval version will be used as an indicator of working memory performance. The PASAT is an auditory task in which subjects are exposed to single digit numbers voiced every three seconds. After each number presentation, the subject's task is to respond with the sum of the last two digits presented. As each new number is presented, the subject must recall the previous digit, add them together, and respond before the next number is presented.

The Multiple Sclerosis Functional Composite (MSFC)²³ is a composite measure incorporating aspects of cognition, walking speed and manual dexterity. The 25-foot walk, 9-hole peg test, and PASAT 3-sec (described above) are normalized based on an established normative sample and an overall composite z- score is then determined. This composite is frequently used as a primary outcome in clinical trials as it covers three major domains of function potentially impaired in MS.

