The Brief Visuospatial Memory Test Revised (BVMTR)^{26,27} is a measure of episodic memory. This task presents a display of six visual designs presented on an 8.5 x 11 piece of paper for three consecutive learning trials. During each trial the stimulus is presented for 10 seconds, after which the participant is asked to draw the figures as accurately as possible in their correct locations. The six designs receive a score of 0, 1, or 2 based on accuracy and location. After a 20-25 minute delay, participants are again asked to recall and draw the designs.

The North American Adult Reading Test (NAART) is a measure of verbal ability. Patients are asked to read a list of words aloud.

Secondary measures will include: self and informant ratings of cognitive problems using the Multiple Sclerosis Neuropsychological Questionnaire,²⁸ the Expanded Disability Status Scale,²⁹ the Multiple Sclerosis Impact Scale, the Beck Depression Inventory – Fast Screen, and subscales from the Sickness Impact Profile³⁰ (an assessment of health related quality of life and activities of daily living). Incidence of adverse events and concurrent medications will also be recorded as potential covariates.

8.2 Describe any primary or secondary safety endpoints.

N/A

[figure not shown]

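### The BVMT-R drawings, a primary measure rated by judgement, can be scored with patient, visit and group in view; they should be coded and shuffled before scoring

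*Combined protocol and SAP*

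**What the plan says.** Section 7.1 sets the design: "This is a prospective, open-label study of Acthar administered as treatment for an acute cognitive relapse". Section 8.1 names four primary measures: "Primary measures will include: Symbol Digit Modalities Test,¹⁴ Brief Visualspatial Memory Test- Revised,¹⁵ Paced Auditory Serial Addition Test,¹⁶ and the Multiple Sclerosis Functional Composite (MSFC).²³" It describes the BVMT-R as three learning trials and a delayed recall, all drawn on paper, and gives the rating rule: "The six designs receive a score of 0, 1, or 2 based on accuracy and location". It does not say whether the learning total or the delayed recall is the primary score.

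On who handles the tests, section 9.2 says "Examining technicians will be responsible for administering the neuropsychological testing battery" and states no masking for them. Section 11.1 says "Data will be processed by trained research assistants blind to study hypotheses". Section 11.5 says "After data scoring and entry, neuropsychological testing files will be de-identified by blacking out identification information". Section 11.3 says "Participants will be assigned study identification numbers at enrollment".

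On the analysis, section 11.1 calculates Cohen's d from day 0 to day 90 within each group. It also uses analysis of variance "to compare the magnitude of change between day 0 and 90 between the MS patients treated with Acthar and the previously collected controls". Section 23.2, by contrast, has 30 stable controls enrolled.

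Two other places might be read as masking and are not. Sections 10.1 and 24.1 mention de-identified charts, but they concern storage. In section 9.2 one person gives the screening SDMT and another looks up the earlier score; that covers eligibility, not outcome scoring.

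**The concern.** Rating a drawing 0, 1 or 2 on accuracy and location leaves room for judgement at the margin. A scorer who can see that a sheet is a treated patient's day-90 visit may give the benefit of the doubt more readily than on the day-0 sheet. In an open-label study that shift would look like recovery on a primary measure.

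Blinding to hypotheses guards against this only in part. Improvement after treatment of a relapse is easy to guess without being told the hypothesis. Section 9.2 also has the coordinator or a designated team member explain the study objectives to participants, and section 20.3 lists one full-time coordinator and two part-time team members. In so small a team, the people who score may also consent or test patients.

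**Working it through.** **The text side by side**

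1. Order of steps: section 11.5 puts scoring and data entry before the removal of identifiers. Identifying information is therefore on the file when it is scored.
2. Scope of blinding: section 11.1 covers hypotheses only. No section hides visit or group from a scorer.
3. Who scores: section 11.1 does not say whether processing includes scoring. If it does, the scorers are blind to hypotheses only. If the examining technicians score, no blinding at all is stated for them. Patient, visit and group can be visible either way.

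**Where leniency would enter**

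Let b_A and b_C be the average leniency at day 90 relative to day 0 in the Acthar and control groups.

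- Within-group change, Acthar: true change + b_A. The bias is b_A.
- Difference in change, Acthar minus control: true difference + (b_A − b_C). If b_A = b_C the bias cancels; if control sheets were scored before this study, the two need not be equal.

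**The plan's own figure**

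Section 11.2 gives d = .56, 30 participants and power above 85%; section 11.1 gives alpha 0.05 without sidedness. For a two-sided paired test by the normal approximation, power is Φ(d√n − 1.96) = Φ(0.56 × √30 − 1.96) = Φ(3.07 − 1.96) = Φ(1.11) = 86.6%. The noncentral t gives 84.2%. The stated figure is thus close to a within-group test. A 30 v 30 comparison does not reproduce it (58.3% normal, 56.9% t). The within-group change is the contrast that b_A enters in full.

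**Illustration in points (all assumed except the rating rule)**

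- If the endpoint is total learning, the maximum is 6 designs × 2 points × 3 trials = 36 points.
- If leniency is 0.5 to 1 point per 12-point trial, it adds 0.5 × 3 = 1.5 to 1 × 3 = 3 points.
- If the SD is 6 to 8 points, this is 1.5/8 = 0.19 to 3/6 = 0.50 SD.
- If delayed recall is the endpoint, the maximum is 6 × 2 = 12 points and the 36-point base does not apply.

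**Illustration in error rate (shift assumed, no true change)**

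For a shift b in SDs of the change score, the two-sided 5% test is evaluated with a noncentral t. The noncentrality is b√30 with 29 df within the group, and b/√(1/30 + 1/30) with 58 df between groups. The between-group column assumes that the whole shift falls on the Acthar group.

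| Assumed shift b | Within group, n = 30 | 30 v 30 |
|---|---|---|
| 0.1 | 8.3% | 6.7% |
| 0.2 | 18.5% | 11.9% |
| 0.3 | 35.5% | 20.8% |

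The documents give no estimate of any such shift.

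**The case against.** Several objections stand and limit the point.

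- A reader might infer that section 11.5 is a masking step placed in the wrong order. The documents do not support that. It answers a form question on data handling and is most naturally a confidentiality step, aimed at personal identifiers. Moving it earlier would hide names but not visit or group, so masking needs an added procedure.
- A reader might set 0.19 to 0.50 SD against the planning d of .56 and conclude that the bias could account for most of the effect. The leniency, the SD and the 36-point endpoint are all assumed, and section 11.2 names neither the test nor the standardiser behind .56. The two are not shown to be on the same scale.
- A reader might infer that drift always distorts the control contrast. Drift that is equal in both groups cancels there.
- Only one of four primary measures benefits. Live testing by unmasked examiners in an open-label study is untouched.
- A reader might infer that masking is almost free. The documents give no costs, and with few staff a scorer with no contact with a given patient may be hard to find.

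The objection that blinding to hypotheses is enough does not stand. It does not hide visit or group, and the text does not show that it covers the people who score. Nor does the cancelling argument remove the problem: the within-group effect has no control to cancel against, and section 11.1 describes the controls as already collected.

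**Conclusion.** The concern holds in a limited form. As written, a primary measure rated by judgement can be scored with patient, visit and group visible in an open-label study. Visit-related leniency would bias the within-group day 0 to day 90 change. It would bias the comparison with controls to the extent that it differs between groups, which is plausible if their drawings were scored before this study.

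The documents do not show that such leniency occurs, and its size cannot be derived from them; the point and error-rate figures are illustrations. No sample size, power or alpha value changes. The plan should be amended because the bias is avoidable for paper drawings, not because a particular amount of bias has been demonstrated.

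**What to change.** In section 11.5, add a masking step before BVMT-R scoring:

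- Replace name, visit date, day 0 or day 90 label and group on each sheet with a code. This must be a sheet-level code, because the study number given at enrollment would link a patient's two visits.
- Shuffle the sheets across visits and groups.
- Have an existing research assistant who did not test that patient and does not hold the key score them in batches.
- Include stored control sheets for masked rescoring where they are available. Where they are not, state that the control contrast on BVMT-R is not masked.

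Section 11.1 should say who scores and what they are masked to. Sections 11.1 and 23.2 should be reconciled on whether controls are already collected or newly enrolled, since this decides whether rescoring is needed.

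The cost is modest handling time, scores that arrive in batches rather than at once, and possibly the rescoring of control sheets. The step does nothing for SDMT, PASAT or the timed walk and peg components of the MSFC, which are scored live; the report should say so.
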